- vi) A significant improvement in symptoms of angina as measured by the Rose Questionnaire
- vii) A significant improvement in quality of life as measured by the LASA Questionnaire, symptoms of depression as measured by the PHQ-9 Questionnaire, and symptoms of stress as measured on the Perceived Stress Scale
- viii) No significant difference in blood levels of creatinine kinase across time
- viii) A significant improvement in sensorimotor characteristics (visual-motor reaction time, peak knee muscular force, muscular force steadiness, standing balance, and overhead squatting posture)
- ix)

Methods

Trial Design

This study will consist of a **blinded randomized controlled prospective study design**, and will include 80 healthy individuals who are employees at Mayo Clinic, Rochester MN.

Excluded subjects will consist of:

- Subjects under the age of 18
- Pregnancy/or suspected pregnancy
- Subjects with a history of liver or kidney disease, acute illness, taking medications (such as glucocorticoids)
- Subjects who have conditions (such as chronic inflammatory muscular diseases or Cushing's syndrome) that affect muscle mass

- Individuals with pacemakers and implantable cardiac defibrillators
- Individuals who conduct any other type of resistance training (> 45 minutes/week)
- Individuals who have regular “high” alcohol consumption (> 80g/day on 5 days a week), or are under acute influence of alcohol, drugs narcotics, and/or painkillers
- Subjects unable to consent to or participate in the 16-week EMS intervention or be available for follow up (1).
- Subjects who report recent surgeries
- Cardiac arrhythmias
- Active medical implants
- Epilepsy
- Seizures
- Severe circulatory disorders
- Arterial circulatory disorders
- Strong bleeding tendencies (hemophilia)
- Bleeding
- Abdominal wall hernia
- Inguinal hernia
- Tuberculosis
- Tumor diseases
- Arteriosclerosis in advanced stage
- Severe neurological disorders
- Diabetes mellitus
- Febrile diseases
- Acute bacterial or viral infections
- Liver diseases
- Kidney diseases
- Cardiovascular diseases
- Coronary heart diseases
- Infected or wounded areas of the skin
- Skin cancer
- Rhabdomyolysis

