Previous studies have demonstrated dependence of the RH-PAT score on nitric oxide, confirming that reported RH-PAT scores indeed reflect changes in nitric oxide– dependent endothelial function, rather than neurohormonal activation (15). The reactive hyperemia protocol will consist of a 16-minute reactive hyperemia test, in the following sequence. A five-minute baseline measurement, after which a blood pressure cuff on the test arm will be inflated to 60 mmHg above baseline systolic blood pressure, or at least 200 mmHg for five minutes (occlusion of pulsatile arterial flow will be confirmed by the reduction of the PAT tracing to zero) after which, the cuff will be deflated, and the post-deflation PAT tracing will be recorded for an additional six minutes. The ratio of the PAT signal after cuff release compared to baseline will be calculated through a computer algorithm automatically normalizing for baseline signal, and indexed to the contralateral arm. The calculated ratio reflects the RH-PAT score (scores below 1.7 will be considered consistent with abnormal peripheral endothelial function).

Although RH-PAT scores may not be the gold standard for endothelial function, several studies have shown good correlation between these methods and more widely accepted methods of

endothelial function testing, such as intra-arterial acetylcholine infusion and brachial artery Doppler ultrasound following reactive hyperemia (11, 13, 14).

Laboratory Testing: Laboratory testing will be undertaken in all participants at baseline, and at 16-weeks follow-up in both the intervention and control group. Venous blood will be drawn for high-sensitivity CRP, uric acid, fasting glucose, HbA1c, lipid panel, lipoprotein A, homocysteine and fibrinogen. For patients in both groups, venous blood will also be tested for creatinine kinase levels at baseline, 8-weeks (halfway into the training programs), and 16-weeks (after completing each respective training program for both groups). A blood sample of approximately 30 mL will be drawn and all samples will be sent to the Mayo Clinic central laboratory for analysis.

Body Weight, Height, and Waist Circumference: Body height, weight and waist circumference will be measured using calibrated devices. Body mass index will be calculated as mass (kg)/height (m²).

VO2 MAX and Maximal Heart Rate: This will be tested using exercise treadmill testing in the conventional manner.

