This will be a randomized controlled trial in which there will be an interventional group and a control group into which individuals will be randomly assigned in a 1:1 ratio. We will match individuals, a priori, as best as possible on age (within 5 years) and sex. Baseline, demographic and risk factor distribution will be outlined in Table 1 of our analyses. The following parameters will be measured in all subjects at baseline, and at 16-weeks follow-up (immediately after completing training in either study protocol depending on which group the participant is in): peripheral endothelial function measured with RH-PAT using EndoPAT; body weight and body mass index; waist circumference; blood pressure; total cholesterol, low and high density

lipoprotein cholesterol and triglycerides, fasting blood glucose and HbA1c; high sensitivity-CRP, uric acid, fibrinogen, homocysteine and lipoprotein A; percentage body fat; maximum strength and maximum power in leg press; VO₂ maximum, maximal heart rate, and scores measured on the Rose questionnaire, LASA questionnaire, PHQ-9 questionnaire and Perceived Stress Scale. In addition, serum creatinine kinase will be measured at baseline, 8 weeks and 16 weeks.

We will compare values of each parameter between groups at baseline and after 16-weeks using unmatched analyses (using Student's t-test when comparing the aforementioned measures as continuous variable and using Chi-squared test when characterizing variables in categories of normal vs. abnormal). We will also assess for differences in the value of each parameter within groups between baseline and 16-weeks follow-up using matched analyses (using Student's paired t-test when comparing the aforementioned measures as continuous variable and McNemar's test when characterizing variables in categories of normal vs. abnormal). Lastly, we will compare the differences between baseline and 16-weeks follow-up for each parameter between groups using unmatched analyses (using the student t-test when comparing the aforementioned measures as continuous variable and using Chi-squared test when characterizing variables in categories of normal vs. abnormal).

Clinical Significance

Cardiovascular disease (CVD) is the primary cause for morbidity, mortality, and the associated rising health care costs in the world (21). According to 2012 statistics, poor diet, smoking, and

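### No log-scale analysis is specified for hs-CRP, lipoprotein A and triglycerides; if these markers are right-skewed and effects are proportional, the planned t-test on changes loses power

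*Combined protocol and SAP*

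**What the plan says.** The Statistical Analysis section lists the parameters measured at baseline and 16 weeks. They include "high sensitivity-CRP, uric acid, fibrinogen, homocysteine and lipoprotein A", and the lipids, among them triglycerides ("lipoprotein cholesterol and triglycerides, fasting blood glucose and HbA1c"). The Laboratory Testing paragraph under Outcomes and Measurements confirms the blood panel.

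Three comparisons are then planned for each parameter:

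- Between groups at each time: "We will compare values of each parameter between groups at baseline and after 16-weeks using unmatched analyses", with Student's t-test for continuous measures.
- Within group: "using Student's paired t-test when comparing the aforementioned measures as continuous variable".
- Between groups on the change from baseline: "using the student t-test when comparing the aforementioned measures as continuous variable".

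The only alternative is a split into normal and abnormal, "using Chi-squared test when characterizing variables in categories of normal vs. abnormal", with McNemar's test within group. No cut-offs are given for these three markers. No log transformation, rank method, normality check or covariate adjustment for baseline appears. The plan does not say that values stay untransformed; that is the natural reading of a plan that names no transformation.

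The Trial Design section says the study "will include 80 healthy individuals who are employees at Mayo Clinic, Rochester MN". Randomization is 1:1, so there are at most 40 per arm.

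**The concern.** Concentrations of these markers cannot fall below zero. If their distribution is right-skewed, a few participants with high values dominate the spread of the untransformed change. The SD in the t-statistic is then set largely by those few, and so is the reported mean difference. The t-test would still hold its error rate under the null, but it would be a weak test of a proportional effect. With 40 per arm there is little power to spare. The markers belong to secondary aim ii and hypothesis iii, so what is at stake is a missed effect on a stated secondary objective, and an estimate that describes few of the participants. A scale chosen after the data have been seen would also be an avoidable analyst choice.

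**Working it through.** **Inputs from the documents.** 80 participants, 1:1, so n = 40 per arm; Student's t-test on the change. The documents contain no power calculation, so there is no stated figure to reproduce.

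**Assumptions.** Two-sided alpha 0.05; no dropout; lognormal marker with log-scale SD s from 0.3 to 1.2; baseline to week-16 correlation r on the log scale from 0.5 to 0.9; the effect multiplies the marker by a constant ratio.

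**Step 1: size the effect so that the log-scale test has 80% power.**

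- Detectable difference in SD units: (1.960 + 0.842) × √(2/40) = 0.626.
- SD of the log change: s × √(2(1 − r)). At s = 1.0 and r = 0.7 this is √0.6 = 0.775.
- Difference on the log scale: 0.626 × 0.775 = 0.485, so the ratio is exp(−0.485) = 0.62.

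**Step 2: simulate both tests.** 20,000 trials per row, r = 0.7, t-test on change:

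| s | Ratio | Power, log | Power, untransformed | Relative loss |
|---|---|---|---|---|
| 0.3 | 0.86 | 79% | 73% | 8% |
| 0.5 | 0.78 | 79% | 64% | 19% |
| 0.8 | 0.68 | 79% | 50% | 37% |
| 1.0 | 0.62 | 79% | 40% | 50% |
| 1.2 | 0.56 | 79% | 32% | nearly 60% |

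Relative loss is 1 − (untransformed/log), from unrounded powers; at s = 1.0 it is 1 − 0.399/0.792 = 0.50. Results at r = 0.5 and 0.9 are nearly the same. With 32 per arm, s = 1.0 and the effect re-sized to keep the log test at 79%, the untransformed test has 39%.

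**Step 3: the other two planned comparisons**, log versus untransformed, r = 0.7, each effect again sized for about 80%. The loss is smaller.

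- Week-16 values alone: 80% vs 74% at s = 0.5; 79% vs 60% at s = 1.0.
- Paired within group: 78% vs 70% at s = 0.5; 78% vs 50% at s = 1.0.

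**Step 4: fixed effects instead of fixed power** (r = 0.6, change score). Repeat runs agree within about three percentage points.

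| Reduction | s | Untransformed | Log | Log, adjusted for log baseline |
|---|---|---|---|---|
| 30% | 0.6 | 64% | 84% | 90% |
| 30% | 0.8 | 36% | 59% | 69% |
| 30% | 1.0 | 21% | 43% | 50% |
| 10% | 0.5 | 15% | 18% | not run |
| 10% | 1.0 | 6% | 8% | not run |

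Normal-theory check at s = 1.0, 30% reduction: ln(1/0.7) = 0.357; SD of log change = √0.8 = 0.894; 0.357/(0.894 × 0.2236) = 1.78; power ≈ Φ(1.78 − 1.96) = 43%.

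**Step 5: type I error.** With no effect, the untransformed change-score test rejects in 3.9% to 5.1% of trials and the log test in about 5%.

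**Step 6: additive model.** Take a lognormal baseline with median 1, normal noise in the change with SD 0.2, and a constant absolute shift. The order reverses: untransformed 78% vs log 60% at baseline s = 0.5, and 78% vs 49% at s = 1.0.

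**The case against.** Every input that drives the loss lies outside the documents. They neither describe these markers as skewed nor give an SD, and no value of s can be assigned to any one marker. The sample is also restricted: healthy employees, with acute illness, infection, diabetes, and liver, kidney and cardiovascular disease excluded, which plausibly trims the upper tail. A 30% reduction from one 20-minute session a week against an exercising sham is not supported by anything in the plan; at 10% both tests have little power and the scale hardly matters. The plan also has a normal/abnormal analysis that extreme values cannot dominate.

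Most of this stands as a limit on size. It does not remove the gap. The normal/abnormal split has no stated cut-offs for these markers and discards information, so it does not recover the lost power.

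Four stronger readings are tempting, and the documents support none of them.

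- A reader might infer that half the power is the most that can be lost, or that it applies to all three markers. The loss runs from 8% to nearly 60% over the assumed range.
- A reader might infer that the log scale is better whatever the distribution. Step 6 shows the reverse under additive effect and noise. A proportional model is reasonable for a quantity that cannot go below zero, but it remains an assumption.
- A reader might infer that hypothesis iii depends on these three markers. It also covers the rest of the lipid profile, glucose, HbA1c, uric acid, fibrinogen and homocysteine.
- A reader might infer that the planned tests are invalid. Step 5 shows that their false-positive rate is at or below nominal.

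**Conclusion.** The concern holds as a conditional loss of power on some secondary endpoints. The plan applies the t-test to hs-CRP, lipoprotein A and triglycerides with no provision for skewed data. If a marker is lognormal and the effect proportional, the change-score test loses about a fifth of its power at a log-scale SD of 0.5 and about half at 1.0, relative to the same test on logs. The loss is minor at 0.3, and in absolute terms it is small whenever the true effect is small. The primary EndoPAT analysis is not touched. Confidence is moderate, because skewness, correlation and effect size are all assumed. The change is still worth making: it uses only data already collected, and it settles the scale before results are seen.

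**What to change.** In the Statistical Analysis section, state that hs-CRP, lipoprotein A and triglycerides are log-transformed. Compare the arms on the log week-16 value adjusted for log baseline, report the ratio of geometric means with a 95% CI, and give untransformed medians and quartiles as description.

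This combines two changes. In the 30% example at s = 1.0, the log scale raises power from 21% to 43%, and baseline adjustment raises it further to 50%.

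The cost is a short addition to the text, with no new data, visits or participants. Results are read as percentage changes instead of differences in concentration, and some power is lost if the effect is in fact additive.

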and guided by two certified instructor (i.e., two applicants coached by one instructor). Whole body-EMS will be conducted on approximately the same day, once a week (i.e., $1.0 \times \text{week}$) for 20 minutes. The device will apply a bipolar electric current; we will select an impulse frequency of 85 Hz, an impulse width of 350 μs , and will apply an interval approach with 4 seconds of stimulation alternating with 4 seconds of rest. Gentle slight dynamic exercises will be performed during the 4-second stimulation phase. Each session will consist of 10–14 dynamic exercises structured in one to two sets of eight repetitions performed without any additional weights in a standing position. Most exercises will be based on a low amplitude squat exercise ($< 35^\circ$ leg flexion) with full amplitude movements of the arms (such as rowing, lat pulley, or butterfly). The emphasis of the protocol however will not be the effect on muscles induced by voluntary activation but by the application of whole body-EMS with high current intensity during functional movements. During the course of the study, the instructor will progressively increase the volume of stimulation by extending the length of the session from 14 up to 20 minutes after 4 weeks of training. The intensity of the stimulation will be regulated using a rate of perceived exertion (RPE) scale to generate a sufficient, but tolerable, intensity of EMS application to all stimulated areas. For each of the muscle groups stimulated, participants will be encouraged to exercise at a RPE of “6–7 out of 10” (i.e., “hard+ to very hard”) on the Borg CR10 Scale (5). This specification will be achieved in close interaction between the participant and instructor. Based on initial start settings determined after 4, 8, and 12 weeks, the impulse intensity will be increased slightly every 3 minutes to maintain/slightly increase the prescribed RPE during each session (**refer to Supplemental Video**).

Schedule of events

| | Baseline Day 0 | Weeks 1-7 | Week 8 follow-up (+/- 7 days) | Weeks 9-15 | Week 16 follow-up (+/-7 days) |
|---|----------------|-----------|-------------------------------|------------|-------------------------------|
| Informed Consent | X | | | | |
| Brief review of medical history | X | | | | |
| Exercise with EMS device | X | X | X | X | X |
| Blood draw and laboratory testing** | X | | | | X |
| Creatinine Kinase | X | | X | | X |
| Physical Assessment* | X | | | | X |

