Peripheral Endothelial Function: Endothelial function will be measured via the RH-PAT index as previously described (6-9). The studies will be performed in a designated quiet, temperature controlled and uniformly lit room. Individuals in the interventional and control groups will be tested at baseline, and will undergo re-testing after completing 16-weeks of training within their assigned arm (within 2 weeks of completion). Subjects will be fasting for 4 hours before the study and will abstain from coffee or tobacco use on the day of the examination. Subjects taking any vasoactive medications, including calcium channel blockers, nitrates, ACE-inhibitors or beta blockers, will discontinue these for 24 hours prior to testing. The study will be conducted in the sitting position in a comfortable chair with armrests. A fitted blood pressure cuff will be placed on one arm, and the finger cuffs of the Endo-PAT 2000 device (Itamar Medical Inc. Ltd., Caesarea, Israel) will be placed on one finger of each hand (10). Subjects will relax for 10 minutes before initiation of the protocol. Baseline blood pressure and heart rate will be obtained via a digital automated blood pressure cuff (Omrom Healthcare, Inc., Vernon Hills, Illinois). The EndoPAT 2000 will be used specifically in this study because it is a Food and Drug Administration–approved noninvasive device, it allows continuous recording of the signal, and interpretation of the data is operator independent. The use of a control arm will allow the elimination of systemic interference of the test and independence from the participant’s knowledge or conscious control of the signals (10-14). The finger probes consist of inflatable latex air cuffs connected by pneumatic tubes to an inflating device controlled through a computer algorithm. A constant counter pressure

(predetermined by baseline diastolic blood pressure) will be applied through the air cushions. This prevents venous pooling and thereby venoarteriolar reflex vasoconstriction while not occluding arterial blood flow. Pulsatile volume changes of the distal digit induce pressure alterations in the finger cuff, which are sensed by pressure transducers and transmitted to and recorded by the Endo-PAT device. A decrease in the arterial blood volume in the distal fingertip causes a decrease in pulsatile arterial column changes, reflected as a decrease in the measured PAT signal, and vice versa.

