An important issue that has arisen with EMS training is the potential risk of elevation in blood creatinine kinase levels. Studies investigating the effects of EMS on creatinine kinase levels have shown that the electrical stimulus from EMS can cause significantly more stress to the muscular system and therefore could lead to higher creatinine kinase levels compared to voluntary muscle contraction exercise (88, 91). Indeed, due to the ability to innervate large muscle areas simultaneously with dedicated individual intensity to each muscle group, EMS can be associated with potential muscle injury. One study showed that, compared to traditional strength training, the stress on the muscular system is about 40% higher after intensive EMS (88). The authors arrived at the conclusion that the level of stimulation intensity is responsible for the elevation in creatinine kinase, while the duration of stimulation had no influence. The authors also showed that subjects still exhibited high values after long periods ranging from 24 hours to 4 days. Further stimulation within this time of decomposition would result in a cumulative rise in creatinine kinase levels (88), which in turn could overstress the muscular system further. Further, one study in which whole body EMS was implemented to the point of exhaustion in healthy novices confirmed very high elevations in creatinine-kinase levels. Although this study did not detect any of the reported clinical consequences of this “severe” rhabdomyolysis, in less fit subjects who are neither optimally prepared nor supervised, initial whole body EMS to exertion may have more far-reaching consequences. Consequently, EMS requires a greater interval between training sessions to prevent overstressing the muscular system and to ensure strength adaptations compared to conventional training. Of note, a subsequent whole body EMS conditioning phase of 10 weeks completed by a second EMS test application to exhaustion demonstrated creatinine-kinase peaks in the range of conventional resistance exercise

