1. During the training session, the trainer or the trained and qualified personnel should concentrate exclusively on the interests of the user(s). Before, during and after training the trainer verbally and visually checks the user's condition so as to rule out health risks and ensure effective training. Training is to be stopped immediately if there are any contraindications. A trainer can train a maximum of 2 people at the same time with EMS.
2. During training, the equipment's operating controls must be directly in reach of the trainer and the user at all times. Operation/adjustment must be simple, quick and precise.

Exercise and Endothelial Dysfunction

Greater than $> 40\%$ of the risk reduction associated with exercise cannot be explained by changes in conventional risk factors. This suggests a cardioprotective vascular conditioning effect of exercise that is characterized by enhanced nitric oxide vasodilator function, altered vascular structure and improved vascular reactivity (93, 94). Sedentary behavior has also been shown to impair endothelial function (95-98). Endothelial dysfunction is the unique yet almost universal “response to injury” of the vasculature under various clinical circumstances (99, 100). It represents the first stage of atherosclerosis, and in fact, relates to plaque progression and vulnerability as well as a several fold increased risk of ischemic cardiac events and stroke (101-106). In clinical practice it is most often recognized by an abnormal vasodilatory response to increased flow (shear stress) or endothelial-dependent vasodilating agents such as acetylcholine

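### The plan names harms of EMS but records adverse events at no visit and in no analysis, and observation after the last session is not guaranteed

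*Combined protocol and SAP*

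**What the plan says.** All references are to the combined protocol and SAP.

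- **Risks.** Efficacy and Safety Considerations links EMS to possible muscle injury, to very high CK after training to exhaustion in novices, and to muscle soreness. (The documents write creatinine kinase.) On how long CK stays raised: "The authors also showed that subjects still exhibited high values after long periods ranging from 24 hours to 4 days". Guidelines for safe and effective WB-EMS adds possible renal stress.
- **Sessions.** The Schedule of events has the row "Exercise with EMS device | X | X | X | X | X". Its five columns run from Baseline Day 0 to "Week 16 follow-up (+/-7 days", and there is no later column.
- **CK.** The schedule row is "Creatinine Kinase | X | | X | | X". Laboratory Testing agrees: "venous blood will also be tested for creatinine kinase levels at baseline, 8-weeks (halfway into the training programs), and 16-weeks", the last draw being at "16-weeks (after completing each respective training program for both groups". Neither place gives hours or days since a session.
- **Session check.** Safety aspects during and after training says: "Before, during and after training the trainer verbally and visually checks the user's condition so as to rule out health risks". It does not say that findings are written down. The same guidelines do ask for a written, signed record of the contraindication interview before the first session.
- **Final tests.** Trial Design and Statistical Analysis put them immediately after the programme. The schedule allows seven days either way. For EndoPAT, participants "will undergo re-testing after completing 16-weeks of training within their assigned arm (within 2 weeks of completion". Outcomes and Measurements lets participant and equipment availability decide.
- **Adverse events.** The schedule has no row for them. The four repeated questionnaires are Rose, LASA, PHQ-9 and PSS. Statistical Analysis lists CK but no adverse-event summary.

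**The concern.** A protocol that describes specific harms of its intervention would normally say how those harms are asked about, written down and reported. This one does not. If it is followed exactly, the trial cannot state how many people in either arm had pain, soreness, injury or a related medical visit. Analysts cannot repair that afterwards, because events that nobody recorded cannot be recovered from the efficacy data.

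The timing of the last contact adds a smaller problem. The last session and the closing assessments share the Week 16 column, nothing is scheduled later, and the timing rules differ from section to section. Some participants could be seen for the last time on the day of their final session, before the 24-hour to 4-day period described in the review has begun.

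**Working it through.** The plan gives no calculation on this point, so there is no figure to reproduce. The check is a reading of every place where harm could be recorded, followed by simple counts.

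**1. Where could harm be recorded?**

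| Place in the plan | What it yields | Counts adverse events by arm? |
|---|---|---|
| Schedule of events | Tests, questionnaires, exercise; no adverse-event row | No |
| Questionnaires | Rose (chest pain), LASA, PHQ-9, PSS at baseline and 16 weeks | No; Rose gives some symptom data |
| CK | Three draws per person | No; a laboratory value only |
| Trainer check | Condition looked at around each session | No; no record required |
| Statistical Analysis | Comparisons at baseline, at 16 weeks and of the change | No; Week 8 CK also has no stated comparison |

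**2. How much of the training does CK cover?**

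- Sessions: 16 weeks × 1 per week = 16. Reading the schedule columns at one session per week gives 1 + 7 + 1 + 7 + 1 = 17. The documents do not reconcile these.
- Post-baseline CK draws: 2 (Weeks 8 and 16).
- Largest share of sessions followed by a draw: 2/16 = 12.5%, or 2/17 = 11.8%.
- The Weeks 1-7 column contains exercise only.

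This is an upper limit. With no fixed lag, a given draw may fall before, inside or after the period in which CK would be raised.

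**3. How long after the last session is the last contact?**

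Assume the last session falls at nominal Week 16 and the final tests follow it. Count whole days.

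| Rule | Lags allowed | Lag 0-3 days (ends before day 4) | Lag 4 days or more |
|---|---|---|---|
| Schedule window | 0-7 (8 values) | 4 of 8 | 4 of 8 |
| Two-week rule (EndoPAT) | 0-14 (15 values) | 4 of 15 | 11 of 15 |

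These are counts of permitted days, not probabilities. A lag of 0 is allowed under both rules and is what the immediately-after wording suggests, but neither rule requires it. Every earlier session is followed by another about seven days later, which is beyond the four-day period.

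**4. What would collection buy?**

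With 80 randomised 1:1, each arm has 80/2 = 40 people, or about 40 × 16 = 640 sessions with full attendance. If events were collected and none occurred in 40 people, the one-sided 95% upper limit would be 1 − 0.05^(1/40) = 7.2% per person. This illustrates what the trial could state and is not a forecast. Without collection, no such limit can be given.

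**The case against.** The strongest reply is that harm is less hidden than it looks. Participants are seen weekly by a trainer who asks about and looks at their condition. CK is measured twice after baseline, and the Rose questionnaire is repeated at 16 weeks. The final tests may come up to two weeks after the last session. The review also says that muscle adapts in as little as 3 weeks, and that after 10 weeks of conditioning even EMS to exhaustion gave CK peaks in the range of ordinary resistance exercise. On that account the risk lies early, and the final session is not where to look hardest. Finally, the 24-hour to 4-day figure is background on a laboratory value from a cited review. It is not a follow-up rule of this trial.

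Much of this stands, and it rules out stronger readings. A reader might infer from the shared Week 16 column that harm after the final session, or between sessions, is never captured. The documents do not support that: a shared column is not a shared day, and the weekly check can notice harm. Nor do they support saying that the trial has no harm-related data, since CK and Rose provide some, or that a late event would reach nobody, since consent and contact pages are not in the supplied text. The entry for a cited trial with no adverse effects reported does not show that the trial failed to collect them.

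What the reply does not supply is a record. A check that need not be written down cannot be tabulated. CK at two unspecified lags does not count pain, injury or medical contact. Early risk strengthens the case for asking at every session, because Weeks 1-7 have no CK draw and no harm form.

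**Conclusion.** The point holds in this form: no visit, outcome or analysis records adverse events, so harms that the protocol itself names cannot be counted by arm. Post-baseline CK follows at most 2 of about 16 sessions, at an unstated lag. Observation after the final session is possible but not assured, with a permitted lag of 0 to 14 days under inconsistent rules.

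The missing record is the main defect, and the gap after the last session is secondary. The change should be made, but nothing here shows that participants are unobserved or that harm has occurred.

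The conclusion rests on three assumptions: one session per week, final tests that follow the last session, and no separate adverse-event procedure outside these documents. Institutional reporting of serious events may exist elsewhere, but the plan does not describe systematic counts by arm from it.

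**What to change.** 1. Add an adverse-events row to the Schedule of events, marked in every column.
2. Have the trainer complete one short checklist at each existing session, covering symptoms and medical contact since the last session. Use identical wording in both arms. The documents describe participants and investigators as blinded but do not say whether the trainer is, so fixed questions matter.
3. Add a line to Statistical Analysis: report adverse events by arm.
4. Reconcile the final-assessment timings in Trial Design, the Schedule of events, Peripheral Endothelial Function and Statistical Analysis.
5. Record the time from the last session to each CK draw.
6. Where the final visit falls on the day of the last session or before the cited four-day period has ended, add one brief remote contact after that period to complete the same checklist.

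The cost is one schedule row, a short form, a few minutes per session and at most 80 brief contacts. Collecting these data changes no training parameter.
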